8.1.1.2 Consent and Collection of Specimens for Future Biomedical Research

The investigator or medically qualified designee will explain the future biomedical research consent to the participant, or the participant's legally acceptable representative, answer all of his/her questions, and obtain documented informed consent before performing any procedure related to future biomedical research. A copy of the informed consent will be given to the participant before performing any procedure related to future biomedical research.

8.1.1.3 Consent for PK Substudy

The investigator or medically qualified designee will explain the PK substudy consent to the participant, or the participant's legally acceptable representative, answer all of his/her questions, and obtain documented informed consent before performing any procedure related to the PK substudy. A copy of the informed consent will be given to the participant before performing any procedure related to the PK substudy.

PRODUCT: MK-2060 PROTOCOL/AMENDMENT NO.: 007-04

8.1.1.4 Consent for Quality of Life Questionnaires

At preselected sites, the investigator or qualified designee will explain the QoL questionnaires consent to the participant, or the participant's legally acceptable representative, answer all of his/her questions, and obtain documented informed consent before administration of the QoL questionnaires. A copy of the informed consent will be given to the participant before administration of the QoL questionnaires.

8.1.2 Inclusion/Exclusion Criteria

All inclusion and exclusion criteria will be reviewed at the Screening and Randomization Visits as outlined in the SoA (Section 1.3) by the investigator, who is a qualified physician, to ensure that the participant qualifies for the study.

8.1.3 Participant Identification Card

All participants will be given a participant identification card identifying them as participants in a research study. The card will contain study site contact information (including direct telephone numbers) to be used in the event of an emergency. The investigator or qualified designee will provide the participant with a participant identification card immediately after the participant provides documented informed consent. At the time of intervention randomization, site personnel will add the treatment/randomization number to the participant identification card.

The participant identification card also contains contact information for the emergency unblinding call center so that a healthcare provider can obtain information about study intervention in emergency situations where the investigator is not available.

8.1.4 Medical History

Medical history will be obtained by the investigator or qualified designee with a focus on defining the participant's history of renal disease, cardiovascular morbidities, and bleeding events.

8.1.5 Prior and Concomitant Medications Review

8.1.5.1 Prior Medications

The investigator or qualified designee will review prior medication use, including antiplatelet and anticoagulant medications which are protocol-specified prohibited medications (Section 6.5), and record prior medication taken by the participant within 28 days before starting the study.

8.1.5.2 Concomitant Medications

The investigator or qualified designee will record medication, if any, taken by the participant during the study in accordance with the Data Entry Guidelines. Refer to Section 6.5 for guidelines on concomitant medication use.

8.1.6 Assignment of Screening Number

All consented participants will be given a unique screening number that will be used to identify the participant for all procedures that occur prior to randomization. Each participant will be assigned only 1 screening number. Screening numbers must not be re-used for different participants.

Rescreening is allowed once per participant. Any participant that is rescreened, will retain the original screening number assigned at the initial Screening Visit. Specific details on the Screening Visit/ Visit 1 requirements are provided in Section 8.11.1.

8.1.7 Assignment of Treatment/Randomization Number

All eligible participants will be randomly allocated and will receive a randomization number. The randomization number identifies the participant for all procedures occurring after randomization. Once a randomization number is assigned to a participant, it can never be reassigned to another participant.

A single participant cannot be assigned more than 1 randomization number.

8.1.8 Study Intervention Administration

Study intervention will be administered intravenously to participants during routine hemodialysis sessions. The first 3 study intervention doses will be administered during routine hemodialysis on study Days 1, 3, and 5. This loading period will be followed by a maintenance period. During the maintenance period, participants will receive study intervention on a once weekly schedule beginning on study Day 8 following the specifications within the study pharmacy manual until the participant completes the treatment or is discontinued from the study. Timing of dose administration is found in Section 8.1.8.1.

Some administration of study intervention will take place during routine dialysis sessions that **are not** study visits. Every effort should be made to administer study intervention once weekly on the same day each week (Section 8.11.3).

8.1.8.1 Timing of Dose Administration

Study intervention will be prepared and dosed per the instructions outlined in the study pharmacy manual. All doses of study intervention will be given 30 minutes after initiation of hemodialysis and administered over approximately 60 minutes.

8.1.9 Discontinuation and Withdrawal

Participants who discontinue study intervention prior to completion of the treatment period should be encouraged to continue to be followed for all remaining study visits as outlined in the SoA and Section 8.11.6.

Participants who withdraw from the study should be encouraged to complete all applicable activities scheduled for the Discontinuation Visit at the time of withdrawal. Any AEs that are

present at the time of withdrawal should be followed in accordance with the safety requirements outlined in Section 8.4.

8.1.9.1 Withdrawal From Future Biomedical Research

Participants may withdraw their consent for future biomedical research. Participants may withdraw consent at any time by contacting the investigator for the main study. If medical records for the main study are still available, the investigator will contact the Sponsor using the designated mailbox ([contact]). Subsequently, the participant's consent for future biomedical research will be withdrawn. A letter will be sent from the Sponsor to the investigator confirming the withdrawal. It is the responsibility of the investigator to inform the participant of completion of withdrawal. Any analyses in progress at the time of request for withdrawal or already performed prior to the request being received by the Sponsor will continue to be used as part of the overall research study data and results. No new analyses would be generated after the request is received.

In the event that the medical records for the main study are no longer available (eg, if the investigator is no longer required by regulatory authorities to retain the main study records) or the specimens have been completely anonymized, there will no longer be a link between the participant's personal information and their specimens. In this situation, the request for specimen withdrawal cannot be processed.

8.1.10 Participant Blinding/Unblinding

STUDY INTERVENTION IDENTIFICATION INFORMATION IS TO BE UNMASKED ONLY IF NECESSARY FOR THE WELFARE OF THE PARTICIPANT. EVERY EFFORT SHOULD BE MADE NOT TO UNBLIND.

For emergency situations where the investigator or medically qualified designee (consistent with local requirements) needs to identify the intervention used by a participant and/or the dosage administered, he/she will contact the emergency unblinding call center by telephone and make a request for emergency unblinding. As requested by the investigator or medically qualified designee, the emergency unblinding call center will provide the information to him/her promptly and report unblinding to the Sponsor. Prior to contacting the emergency unblinding call center to request unblinding of a participant's intervention assignment, the investigator who is a qualified physician should make reasonable attempts to enter the intensity of the AEs observed, the relation to study intervention, the reason thereof, etc., in the medical chart. If it is not possible to record this assessment in the chart prior to the unblinding, the unblinding should not be delayed.

In the event that unblinding has occurred, the circumstances around the unblinding (eg, date, reason, and person performing the unblinding) must be documented promptly, and the Sponsor Clinical Director notified as soon as possible.

Once an emergency unblinding has taken place, the investigator, site personnel, and Sponsor personnel may be unblinded so that the appropriate follow-up medical care can be provided to the participant.

Participants whose treatment assignment has been unblinded by the investigator or medically qualified designee and/or nonstudy treating physician must be discontinued from study intervention, but should continue to be monitored in the study.

Additionally, the investigator or medically qualified designee must go into the IRT system and perform the unblind in the IRT system to update drug disposition. In the event that the emergency unblinding call center is not available for a given site in this study, the IRT system should be used for emergency unblinding in the event that this is required for participant safety.

At the end of the study, random code/disclosure envelopes or lists and unblinding logs are to be returned to the Sponsor or designee.

8.1.11 Calibration of Equipment

The investigator or qualified designee has the responsibility to ensure that any device or instrument used for a clinical evaluation/test during a clinical study that provides information about inclusion/exclusion criteria and/or safety or efficacy parameters shall be suitably calibrated and/or maintained to ensure that the data obtained are reliable and/or reproducible. Documentation of equipment calibration must be retained as source documentation at the study site.

Critical equipment for this study includes, but it is not limited to:

- Infusion pumps
- Vital signs and ECG instruments
- All equipment to process study intervention and samples such as, but not limited to, centrifuge equipment, pipettes, and freezers for MK-2060 or placebo and sample storage.

8.1.12 Identification of External Contact Person

All participants will be asked to identify a person to be contacted by the study site to collect the participant's vital status if the participant cannot be reached (eg, spouse, family, friend, neighbor, etc.).

8.2 Efficacy Assessments

The primary endpoint for the study is the time to first occurrence of AVG thrombosis (Section 4.2.1.1). Study staff is expected to report all AVG thrombosis events as AEs and identify them as potential primary endpoints upon learning of the event's occurrence either during routine care of study participants or at study visits.

Events constituting the tertiary/exploratory endpoint of major thrombotic CV events will be reported as AEs upon study staff learning of these events' occurrence during routine care of

study participants or at study visits. These events include fatal and non-fatal MI, ischemic stroke, PE, DVT, and acute limb ischemia.

At selected study sites, KDQOL-SF and EQ-5D-5L questionnaires will be administered by the interviewer (investigator or qualified designee) at the visits outlined in the SoA. The questionnaires should be administered before administration of study intervention.

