8.4.2 Method of Detecting AEs, SAEs, and Other Reportable Safety Events

Care will be taken not to introduce bias when detecting AEs and/or SAEs and other reportable safety events. Open-ended and nonleading verbal questioning of the participant is the preferred method to inquire about AE occurrence **except for assessment of study endpoints**.

Participants will be directly questioned about the occurrence of AVG thrombosis or major thrombotic cardiovascular endpoints (Section 8.2) at study visits. These events will be reported as AEs or SAEs upon study staff learning of the events' occurrence during routine care of study participants or at study visits

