8.4.6 Disease-related Events and/or Disease-related Outcomes Not Qualifying as AEs or SAEs

Not applicable.

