9.6.2 Analysis Methods for Safety Analyses

Safety and tolerability will be assessed by clinical review of all relevant parameters including AEs, laboratory tests, vital signs, and ECGs. The primary approach to analysis of safety will include all data through treatment including the 3-month follow-up assessment. The analysis will compare safety events in each MK-2060 group to the placebo group.

^a Treatment group and the stratification factors used for randomization will be included in the model as fixed effects.

Adverse Events

AEs will be coded using the standard MedDRA and grouped according to SOC.

The analysis of safety results will follow a tiered approach (Table 4). The tiers differ with respect to the analyses that will be performed.

For the safety analyses, any participant who undergoes a kidney transplant during the study will be censored at 3 months after the date of the kidney transplant.

Tier 1 Events

Safety parameters or AEs of special interest that are identified a priori constitute "Tier 1" safety endpoints that will be subject to inferential testing for statistical significance with p-values and 95% CIs. For this protocol, the time to the composite endpoint of an ISTH major bleeding event or a clinically relevant non-major bleeding event (adjudicated) is a Tier 1 event and will be analyzed following the analysis approach for the primary efficacy analysis.

Tier 2 Events

Tier 2 parameters will be assessed via point estimates with 95% CIs provided for between-treatment differences in the proportion of participants with events.

Membership in Tier 2 requires that at least 4 participants in any treatment group exhibit the event; all other AEs and PDLCs will belong to Tier 3. The threshold of at least 4 events was chosen because the 95% CI for the between-group difference in percent incidence will always include zero when the treatment groups each have fewer than 4 events and thus would add little to the interpretation of potentially meaningful differences. Because many 95% CIs may be provided without adjustment for multiplicity, the CIs should be regarded as a helpful descriptive measure to be used in review, not a formal method for assessing the statistical significance of the between-group differences in AEs and PDLCs.

[figure not shown]

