In addition, summary measures of AEs consisting of the percentage of participants with any AE, with a drug-related AE, with an SAE, with an AE which is both drug-related and serious, who discontinued due to an AE, and who died will be considered Tier 2 endpoints.

For AEs prespecified for adjudication (cardiovascular, AVG thrombotic, bleeding events, and death), results of adjudication are also considered Tier 2 endpoints.

The 95% CIs will be provided for between-treatment differences in the percentage of participants with each Tier 2 event; these analyses will be performed using the M&N method.

Tier 3 Events

Safety endpoints that are not Tier 2 events will be considered Tier 3 events. Only point estimates by treatment group will be provided for Tier 3 safety parameters.

Continuous Safety Measures

For continuous measures such as changes from baseline in laboratory and vital signs parameters, summary statistics for baseline, on treatment, and change from baseline values will be provided by treatment group.

Table 4 Analysis Strategy for Safety Parameters

[figure not shown]
Safety Tier	Safety Endpoint	P-Value for Treatment Comparison	95% CI for Treatment Comparison	Descriptive Statistics
Tier 1	Time to first ISTH major bleeding event or clinically relevant non-major bleeding event (adjudicated)	X	X	X
Tier 2	Any AE		X	X
	Any serious AE		X	X
	Any drug-related AE		X	X
	Any serious and drug-related AE		X	X
	Discontinuation due to AE		X	X
	Death		X	X
	Adjudicated major thrombotic CV events		X	X
	Adjudicated AVG thrombotic events		X	X
	Adjudicated ISTH major bleeding events		X	X
	Specific AEs, SOCs, PDLCs (incidence ≥4 of participants in 1 of the treatment groups)		X	X
Tier 3	Specific AEs, SOCs, PDLCs (incidence <4 of participants in all the treatment groups)			X
	Change from baseline results (laboratory tests, ECGs, vital signs)			X

AE=adverse event; AVG=arteriovenous graft; CI=confidence interval; CV=cardiovascular; ECGs=electrocardiogram(s); ISTH=International Society on Thrombosis and Haemostasis; PDLC=predefined limit of change; SOC=system organ class; X=results will be provided.

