10.3.2 Definition of SAE

If an event is not an AE per definition above, then it cannot be an SAE even if serious conditions are met.

An SAE is defined as any untoward medical occurrence that, at any dose:

a. Results in death

b. Is life-threatening

• The term "life-threatening" in the definition of "serious" refers to an event in which the participant was at risk of death at the time of the event. It does not refer to an event, which hypothetically might have caused death, if it were more severe.

c. Requires inpatient hospitalization or prolongation of existing hospitalization

Hospitalization is defined as an inpatient admission, regardless of length of stay, even
if the hospitalization is a precautionary measure for continued observation. (Note:
Hospitalization for an elective procedure to treat a pre-existing condition that has not
worsened is not an SAE.) A pre-existing condition is a clinical condition that is
diagnosed prior to the use of an MSD product and is documented in the participant's
medical history.

d. Results in persistent or significant disability/incapacity

- The term disability means a substantial disruption of a person's ability to conduct normal life functions.
- This definition is not intended to include experiences of relatively minor medical significance such as uncomplicated headache, nausea, vomiting, diarrhea, influenza,

and accidental trauma (eg, sprained ankle) that may interfere with or prevent everyday life functions but do not constitute a substantial disruption.

e. Is a congenital anomaly/birth defect

• In offspring of participant taking the product regardless of time to diagnosis.

f. Other important medical events

- Medical or scientific judgment should be exercised in deciding whether SAE
 reporting is appropriate in other situations such as important medical events that may
 not be immediately life-threatening or result in death or hospitalization but may
 jeopardize the participant or may require medical or surgical intervention to prevent 1
 of the other outcomes listed in the above definition. These events should usually be
 considered serious.
- Examples of such events include invasive or malignant cancers, intensive treatment in an emergency room or at home for allergic bronchospasm, blood dyscrasias or convulsions that do not result in hospitalization, or development of drug dependency or drug abuse.

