(Note: This criterion is not applicable if: (1) the initial AE resulted in death or permanent disability, or (2) the study is a single-dose drug study; or (3) study intervention(s) is/are used only 1 time.)

NOTE: IF A RECHALLENGE IS PLANNED FOR AN AE THAT WAS SERIOUS AND MAY HAVE BEEN CAUSED BY THE STUDY INTERVENTION, OR IF RE-EXPOSURE TO THE STUDY INTERVENTION POSES ADDITIONAL POTENTIAL SIGNIFICANT RISK TO THE PARTICIPANT THEN THE RECHALLENGE MUST BE APPROVED IN ADVANCE BY THE SPONSOR CLINICAL DIRECTOR, AND IF REQUIRED, THE IRB/IEC.

• Consistency with study intervention profile: Is the clinical/pathological presentation of the AE consistent with previous knowledge regarding the study intervention or drug class pharmacology or toxicology?

- The assessment of relationship will be reported on the case report forms/worksheets by an investigator who is a qualified physician according to his/her best clinical judgment, including consideration of the above elements.
- Use the following scale of criteria as guidance (not all criteria must be present to be indicative of a study intervention relationship).
 - Yes, there is a reasonable possibility of study intervention relationship:
 - There is evidence of exposure to the study intervention. The temporal sequence of the AE onset relative to the administration of the study intervention is reasonable. The AE is more likely explained by the study intervention than by another cause.
 - No, there is not a reasonable possibility of study intervention relationship:
 - Participant did not receive the study intervention OR temporal sequence of the AE onset relative to administration of the study intervention is not reasonable OR the AE is more likely explained by another cause than the study intervention. (Also entered for a participant with overdose without an associated AE.)
- For each AE/SAE, the investigator must document in the medical notes that he/she has reviewed the AE/SAE and has provided an assessment of causality.
- There may be situations in which an SAE has occurred and the investigator has minimal information to include in the initial report to the Sponsor. However, it is very important that the investigator always make an assessment of causality for every event before the initial transmission of the SAE data to the Sponsor.
- The investigator may change his/her opinion of causality in light of follow-up information and send an SAE follow-up report with the updated causality assessment.

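### Optional improvement: the Tier 2 any-serious-AE row in Table 4 counts serious AVG thromboses, so it partly re-measures efficacy; one supportive row would separate the two

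*Combined protocol and SAP*

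**What the plan says.** Table 4 and the Tier 2 text of section 9.6.2 are where this point bites. Tier 2 includes "summary measures of AEs consisting of the percentage of participants with any AE, with a drug-related AE, with an SAE", each with a 95% Miettinen-Nurminen (M&N) interval for the difference from placebo. No exclusion of endpoint events is stated.

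Four other sections determine what enters the SAE row:

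- Section 8.2: "Study staff is expected to report all AVG thrombosis events as AEs and identify them as potential primary endpoints". Taken alone, this covers AEs only.
- Section 8.4.2, on AVG thrombosis and major thrombotic cardiovascular endpoints: "These events will be reported as AEs or SAEs upon study staff learning of the events' occurrence".
- Section 8.4.6, headed "Disease-related Events and/or Disease-related Outcomes Not Qualifying as AEs or SAEs", is marked not applicable, so no endpoint event is exempted.
- Section 10.3.2 makes an event serious if, among other criteria, it "Requires inpatient hospitalization or prolongation of existing hospitalization". A thrombosis is an SAE only if it meets one of these criteria.

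Table 4 also has rows with intervals for adjudicated AVG thrombotic events, adjudicated major thrombotic CV events, adjudicated ISTH major bleeding and death, and for "Specific AEs, SOCs, PDLCs (incidence ≥4 of participants in 1 of the treatment groups"). Section 9.6.2 says of the Tier 2 intervals that "the CIs should be regarded as a helpful descriptive measure to be used in review".

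**The concern.** Safety and tolerability is a secondary objective, and the any-serious-AE row is the overall summary of serious harm. If the drug prevents thrombosis, placebo has more serious thromboses, and the row moves in favour of MK-2060 even when all other serious events are equally common.

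What is at stake is narrow. Adjudicated bleeding (Tier 1), death, and specific-AE and SOC rows without AVG thrombosis do not move. The drug-related rows hardly move, because section 10.3.4 scores an event as unrelated where "the AE is more likely explained by another cause than the study intervention". What could be partly masked is mainly an excess of other SAEs spread thinly over many terms, which only an overall row would show. That matters most if efficacy is met at the interim, when section 4.1 lets the eDMC weigh safety factors before recommending whether to continue.

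**Working it through.** **Inputs from the plan (section 9.9.1):** 171 first AVG thromboses at the final analysis and 103 at the interim, over three arms; 163 per arm; HR 0.6 for each dose.

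**Check of the plan's own figure.** One dose plus placebo takes 171 × 1.6/2.2 = 124.4 events. Schoenfeld power is Φ(√(124.4/4) × |ln 0.6| − 1.96) = Φ(0.89) = 81.3% at one-sided 0.025. Variants (alpha 0.024, the two-look design, an exponential split with 122 pairwise events) give 80.1% to 80.9%. The stated 80% reproduces, so the event counts and HR are consistent.

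**Step 1: thrombosis risk per arm, equal follow-up assumed.** Solve 163 × [p0 + 2(1 − (1 − p0)^0.6)] = E.

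- E = 171: p0 = 44.9% (about 73 of 163), p1 = 30.0% (about 49), gap 14.8 points.
- E = 103: p0 = 27.8%, p1 = 17.7%, gap 10.0 points.

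**Step 2: shift in the any-SAE row when other SAEs are equal in the arms.** Two inputs are assumed because the plan gives neither: f, the share of thromboses that are serious, and s, the risk of any other SAE. Independence is also assumed.

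- First events only: shift = (1 − s) × f × (p0 − p1).
- Recurrences at the first-event hazard, each serious with probability f: shift = (1 − s) × [exp(−0.6fH) − exp(−fH)], with H = −ln(1 − p0) = 0.5951.

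With s = 40% and 171 events, in points favouring MK-2060:

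| f | first events only | with recurrences |
|---|---|---|
| 5% | 0.4 | 0.7 |
| 10% | 0.9 | 1.4 |
| 25% | 2.2 | 3.2 |
| 50% | 4.4 | 5.6 |
| 100% | 8.9 | 8.9 |

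For example, at 25%: 0.6 × 0.25 × 14.8 = 2.2. At 103 events the figures for 25/50/100% are 1.5 to 1.8, 3.0 to 3.4, and 6.0.

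Positive dependence shrinks the shift. With a Gaussian copula correlation of 0.5, the right-hand column at 25/50/100% (final) becomes 1.8, 4.0 and 8.0.

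**Step 3: size against the interval.** At s = 40% and f = 100%, the M&N 95% interval around −8.9 is −18.9 to 1.9. At s = 20% and f = 100%, the shift is 0.8 × 14.8 = 11.9 points and the interval, −22.3 to −0.8, excludes zero. Sampling error therefore usually covers the shift, but not in every case.

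**Step 4: what masking would look like.** Suppose a true 10-point excess of other SAEs on drug, with placebo s from 20% to 40%. Any-SAE risk per arm is 1 − (1 − s)(1 − f·p), first events only. The row then shows:

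- f = 25%: about +6 to +7
- f = 50%: about +3 to +4
- f = 75%: about −1 to +1
- f = 100%: about −5 to −2

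A row without thromboses shows about +10. At placebo s = 20% that is 49 vs 33 of 163, M&N interval 0.4 to 19.2, against −8.1 to 13.0 in the existing row at f = 50%.

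**Step 5: can the printed AVG row simply be subtracted?** No, because a participant with both kinds of event is in both rows. With s = 40% in every arm and f = 100%, the any-SAE risks are 66.9% and 58.0%. Subtracting 44.9% and 30.0% leaves 22.1% and 28.0% (from unrounded values): a false 5.9-point excess on MK-2060 where the true difference is zero.

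**Step 6: data window.** Steps 1 to 5 use counts at the efficacy cutoff, whereas section 9.6 takes the primary safety analysis through the Safety Follow-up Visit. Spreading H over the 10-month median treatment duration (section 4.3.2) and adding 3 months gives a thrombosis gap of 12.4 points if the effect stops with dosing, or 16.7 if it persists. At s = 40% and f = 100%, first events only, the shift is then 0.6 × 12.4 = 7.4 or 0.6 × 16.7 = 10.0, against 8.9.

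**The case against.** The strongest reply is that no error exists. A serious graft thrombosis is a real serious harm, so an all-cause SAE row that counts it estimates what it claims to. Table 4 already shows AVG thromboses, bleeding, major CV events and death separately. It also gives intervals by specific AE and SOC, so an excess in one term stays visible even within the SOC that holds AVG thrombosis. No decision rule uses the row, and its interval is declared descriptive. All of that stands, and it is why this is an optional improvement. It does not supply the missing summary, since the AVG row cannot be subtracted.

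Second, the size rests on inputs the plan lacks. This also stands: nothing bounds the serious share from below, and at 5% to 10% the shift is about 0.4 to 1.4 points.

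Third, the sSAP, eDMC charter and monitoring guidelines are not among the documents and may already contain such a row. That cannot be excluded, so the request is conditional for the eDMC outputs.

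A reader might infer that the safety analysis is biased, or that the plan would hide harm from MK-2060. The documents do not support that: the bleeding, death and term-level rows are untouched. A reader might also infer that every thrombosis counts as an SAE; section 10.3.2 requires a criterion to be met.

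**Conclusion.** The point holds as a low-cost, optional improvement, not as a defect. Serious AVG thromboses enter the any-serious-AE row, and neither Table 4 nor its text offers a version without them.

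The 44.9% vs 30.0% thrombosis risk follows from the plan's own figures plus equal follow-up. The shift in the SAE row runs from under 1 point to about 9 at an assumed 40% risk of other SAEs, depending almost wholly on the unknown serious share. It is smaller with positive dependence and larger if other SAEs are rarer. These sizes hold at the efficacy cutoff if the drug performs as assumed; they are not predictions. It would be too strong to say that the row will mislead, and too weak to say that the shift always lies within sampling error.

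The any-AE row is affected in the same way. All thromboses count there, but if 90% of participants have another AE the shift is only 0.1 × 14.8 = 1.5 points.

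**What to change.** Keep all existing rows. In section 9.6.2 and Table 4, or in the sSAP (section 9 allows that route for non-confirmatory analyses), add one supportive Tier 2 row: participants with at least one serious AE other than an AVG thrombosis confirmed by the Clinical Adjudication Committee. Specify:

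- exclusion at event level, so a participant with another SAE still counts;
- the same M&N interval and the same data window as the existing row;
- major thrombotic CV events kept in, so that thrombotic harm is not hidden.

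Give the row to the eDMC if its outputs do not already include it. Where adjudication lags a review, use site-flagged AVG events and say so.

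Cost: one sentence and one table row. Sites already flag AVG events and the committee already adjudicates them (section 10.1.4.3). Sample size, alpha, power and event reporting to the Sponsor do not change.

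Downsides: two versions of the summary row, and some efficacy signal left from unconfirmed AVG events and from AEs that follow a thrombosis. As an assumed example, take unconfirmed events at 10% to 20% of the confirmed rate, the same HR and 50% to 100% serious. That is an effective f of 5% to 20% in the recurrence formula at s = 40%, which leaves 0.7 to 2.6 points at the final analysis.
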